Official Title of the study: Longitudinal Outcomes of Hearing Aids

NCT number: NCT04030299

Date of the document: 3/9/2022

Study Protocol

Longitudinal Outcomes of Hearing Aids

1 Background

Hearing aids (HAs) have been shown to improve communication ability, hearing-specific quality of life, and social and emotional function. Additionally, HAs have the potential to reduce cognitive decline in older adults at increased risk. Despite these benefits, HA adoption rates remain quite low. The reasons for this low HA adoption rate are multidimensional, with one widely cited reason being the financial and physical barriers to accessing traditional HA fitting services and amplification devices.

In recent years, the over-the-counter (OTC) service-delivery model has emerged as an alternative to traditional HAs. OTC HAs enable users to self-determine hearing loss and self-fit the device without professional support. While previous research exists on the short-term outcomes of OTC HAs, there is no evidence on the long-term outcomes of OTC HAs and whether these outcomes worsen, improve, or remain stable over time.

2 Purpose

To explore the trajectory of long-term outcomes of OTC HAs over a period of twelve weeks.

3 Research Design

3.1 Overview

This study is an observational study. Participants will use OTC HAs for twelve weeks. Outcomes will be measured at the first week, sixth week, and twelfth week post-HA use.

3.2 Intervention

OTC Group: In this group, preset-based OTC HAs, simulated using commercially available HAs, will be provided to subjects. Subjects will take the full initiative and responsibility for learning and using the HAs without assistance from audiologists.

3.3 Sample size

Because this is an exploratory study, no power analysis is conducted to determine the sample size. Based on prior research experience, it is estimated that approximately 34 participants are needed to see the trend of long-term HA outcomes.

3.4 Randomization and blinding

All participants will be assigned to the OTC group. Therefore, blinding will not be necessary.

3.5 Participant eligibility criteria

3.5.1 Inclusion: Inclusion Criteria:

- Adults between 55 and 85 years old
- Adult-onset, bilateral, mild-to-moderate sensorineural hearing loss

3.5.2 Exclusion Criteria:

• Non-native speaker of English

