3.6 Outcome measures

3.6.1 Primary outcome

3.6.1.1 Glasgow Hearing Aid Benefit Profile (GHABP)

The GHABP is a questionnaire that measures hearing aid users' listening experience in four situations (TV listening, small conversation in quiet, conversation in noise, and group conversation). The score ranges from 0 (no benefit) to 5 (lots of benefit). The score at 1-week, 6-week and 12-week post intervention is the primary outcome. Participants will complete this questionnaire at 1-week, 6-week, and 12-week post-intervention based on their experience with the study device.

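### Does Section 3.5's silence on current or former hearing-aid use undermine the 12-week course the study sets out to describe?

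*Protocol*

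**What the plan says.** Section 3.5 of the protocol has two inclusion criteria, "Adults between 55 and 85 years old" and "Adult-onset, bilateral, mild-to-moderate sensorineural hearing loss", and one exclusion, "Non-native speaker of English". Neither this section nor any other mentions earlier hearing-aid use.

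Section 1 (Background) links low uptake of hearing aids to "financial and physical barriers to accessing traditional HA fitting services and amplification devices". The purpose in Section 2 is the trajectory of outcomes with over-the-counter (OTC) devices over twelve weeks, with no restriction to new users. Section 3.2 has participants "learning and using the HAs without assistance from audiologists". Section 3.1 times the assessments at the "first week, sixth week, and twelfth week post-HA use", and Section 3.6.1.1 states: "The score at 1-week, 6-week and 12-week post intervention is the primary outcome".

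Section 3.3 estimates that "approximately 34 participants are needed to see the trend of long-term HA outcomes", without a power analysis. Under Section 3.4 everyone is in the OTC group, and Section 3.7 plans no statistical analysis. The data listed are the outcome measures in Section 3.6 and the adverse events in Section 3.8. There is no section on baseline data.

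**The concern.** The study has one group and no comparator, so its product is a described course from week 1 to week 12. A first-time user may still be adapting at week 1, while someone who has worn aids for years may not be. If both kinds of participant enter, the average course mixes two patterns.

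The rationale in Section 1 seems to point to people who have not yet adopted hearing aids, and Section 3.2 speaks of learning to use the devices without an audiologist. A participant fitted by an audiologist in the past might seem to match that picture only in part. The phrase "first week, sixth week, and twelfth week post-HA use" could also seem to start a different clock for someone who was already using aids.

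Eligibility belongs in the protocol, so the silence cannot be put down to a statistical analysis plan that is not shown. What is at stake is whether a reader can tell whose course is being reported: that of first-time users or that of a mixture.

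**Working it through.** **1. Are prior users eligible?** The criteria in Section 3.5 cover age, type and degree of hearing loss, and language. Prior use is neither required nor excluded. On an ordinary reading, current and former users who meet the criteria may enter, so the population is broad but not undefined.

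**2. Is there more than one visit clock?** The sentence in Section 3.1 just before the assessment times says that participants wear the OTC devices for the twelve-week period, so the hearing aid meant there is the study device. Each outcome in Section 3.6 is likewise tied to the study device. Sections 3.1 and 3.6.1.1 name one clock for everyone.

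**3. Does Section 3.2 describe a new user?** It describes how the study devices are provided and what support is withheld during the study. An experienced wearer who is given a preset-based device and no audiologist fits it fully.

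**4. Does the missing history item show that history is not recorded?** No. Section 3.5 requires age and hearing status to be known at entry, yet no demographic or audiometric item is listed either. Section 3.6 is a list of outcomes, not an inventory of all data collected.

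**5. How far could the pooled course differ from that of first-time users?** Let *f* be the share of prior users, and let *d*₁ and *d*₂ be the mean changes of first-time and prior users.

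Pooled change = (1 − *f*)·*d*₁ + *f*·*d*₂, so pooled − first-time = *f*·(*d*₂ − *d*₁).

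With *r* = *d*₂/*d*₁, this is *f*·(*r* − 1) as a fraction of *d*₁. Both *f* and *r* are assumptions, since the protocol gives neither.

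| *f* | *r* = 0 | *r* = 0.5 | *r* = 1 | *r* = 1.5 |
|---|---|---|---|---|
| 10% | −10% | −5% | 0 | +5% |
| 20% | −20% | −10% | 0 | +10% |
| 30% | −30% | −15% | 0 | +15% |
| 40% | −40% | −20% | 0 | +20% |

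The gap is zero when no prior users enrol or when both groups change alike. Section 1 allows that outcomes may stay stable. If *d*₁ is near zero, the ratio *r* and the percentages lose meaning, and only the absolute form *f*·(*d*₂ − *d*₁) can be used.

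**6. Could a split by prior use show the cause of differing courses?** Take 34 participants from Section 3.3 and express everything in SDs of the change.

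- Mean change: 95% half-width = t(0.975, n − 1)/√n. For the pooled 34 this is 0.349.
- Difference between groups, equal SD assumed: 95% half-width = t(0.975, 32)·√(1/n₁ + 1/n₂).

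| Prior / first-time users | Mean change, prior users | Difference between groups |
|---|---|---|
| 3 / 31 | 2.484 | 1.232 |
| 7 / 27 | 0.925 | 0.864 |
| 10 / 24 | 0.715 | 0.767 |
| 14 / 20 | 0.577 | 0.710 |

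The four splits correspond to about 10, 20, 30 and 40% of 34. Even at 14 against 20, a difference of half an SD would have an interval that includes zero (0.5 − 0.710 = −0.210).

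**The case for a change.** The best argument for a change is that it costs almost nothing: one sentence on eligibility and one question at entry, with sample size, visits and outcomes untouched. Eligibility is fixed by the protocol and by no later document. The adoption rationale in Section 1 makes prior use a natural thing for a reader to ask about, and from the protocol alone that reader cannot tell whether the sample is made up of first-time users or is mixed.

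The textual facts behind this stand, and so does the value of describing the sample. What does not stand is the step from there to a defect. Section 1 gives background, and the purpose in Section 2 is not limited to new users. The claim that differing courses could not be traced to prior use would require that history is not collected, which the protocol does not show. It would also remain largely true with history recorded, given the half-widths above. The added sentence would write down what Section 3.5 already implies, or else narrow the population by choice. Neither corrects an error.

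**Conclusion.** No change to the plan follows. Section 3.5 admits current and former hearing-aid users by not excluding them, and the pooled 12-week course is a sound description of everyone eligible. For that reading the effect is nil.

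For a reader who takes the course as that of first-time users, the gap is *f*·(*d*₂ − *d*₁). Over the assumed ranges it runs from −40% to +20% of the first-time-user change and includes zero. These figures rest wholly on assumed shares and ratios, because nothing in the protocol says that prior users change differently.

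This is missing detail of a kind that investigators ordinarily supply when they describe the sample. Reporting how many participants had worn hearing aids before would help readers, and it needs no revision of the design, the outcomes or the planned description. With about 34 participants and no planned statistical analysis, it would not alter a conclusion. The judgement assumes the ordinary reading of Section 3.5, under which what is not excluded is allowed.

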3.6 Outcome measures

3.6.1 Primary outcome

3.6.1.1 Glasgow Hearing Aid Benefit Profile (GHABP)

The GHABP is a questionnaire that measures hearing aid users' listening experience in four situations (TV listening, small conversation in quiet, conversation in noise, and group conversation). The score ranges from 0 (no benefit) to 5 (lots of benefit). The score at 1-week, 6-week and 12-week post intervention is the primary outcome. Participants will complete this questionnaire at 1-week, 6-week, and 12-week post-intervention based on their experience with the study device.

3.6.2 Secondary outcomes

3.6.2.1 Hearing Handicap Inventory for the Elderly (HHIE) or Hearing Handicap Inventory for Adults (HHIA)

The HHIE and HHIA are questionnaires designed to measure subject's perceived hearing handicap. For subjects order and younger 65 years old, the HHIE and HHIA will be used, respectively. The score ranges from 0 (no handicap) to 100 (more handicap). Participants will complete this questionnaire at 1-week, 6-week, and 12-week post-intervention based on their experience with the study device.

3.6.2.2 Hearing Aid Satisfaction Survey (HASS)

The HASS is a questionnaire developed to measures subject's perceived hearing aid satisfaction. The score ranges from 0 (low satisfaction) to 10 (high satisfaction). Participants will complete this questionnaire at 1-week, 6-week, and 12-week post-intervention based on their experience with the study device.

3.6.2.3 Willingness-to-pay (WTP)

WTP estimates the extent to which (in dollars) a subjects, at a maximum, is willing to pay out-of pocket for the amplification devices and the associated services used in the study. Participants will complete this questionnaire at 6-week, and 12-week post-intervention based on their experience with the study device.

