3.6.2.6 Connected Speech Test (CST)

The CST is a speech recognition test designed to simulate daily speech communication. The score ranges from 0 (understand no speech) to 100 (understand all speech). Participants will complete this test in the laboratory at 1-week, 6-week, and 12-week post-intervention with the study device.

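### Does collecting willingness-to-pay only at weeks 6 and 12 conflict with the week 1, 6 and 12 schedule in section 3.1?

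*Protocol*

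**What the plan says.** Section 2 of the protocol states the aim: "To explore the trajectory of long-term outcomes of OTC HAs over a period of twelve weeks". Section 3.1 (Overview) sets the timing in one sentence: "Outcomes will be measured at the first week, sixth week, and twelfth week post-HA use".

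Section 3.6 then gives each measure its own schedule. For the primary outcome, section 3.6.1.1 says "The score at 1-week, 6-week and 12-week post intervention is the primary outcome". Among the secondary outcomes, the satisfaction survey in section 3.6.2.2 is typical: "Participants will complete this questionnaire at 1-week, 6-week, and 12-week post-intervention based on their experience with the study device". The speech test in section 3.6.2.6 uses the same three weeks.

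WTP, in section 3.6.2.3, is the exception: "Participants will complete this questionnaire at 6-week, and 12-week post-intervention based on their experience with the study device". That section defines the measure as the most a participant "is willing to pay out-of pocket for the amplification devices and the associated services used in the study". It does not say why week 1 is left out.

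**The concern.** Read alone, section 3.1 suggests that every outcome is taken three times, and section 3.6.2.3 departs from that without comment. The two satisfaction scales (HASS and SADL) are completed at week 1 and, like WTP, rest on the participant's use of the device. If one week of use is enough to rate satisfaction, a reader may ask why it is not enough to state a price.

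Two things would be at stake:

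- **Conduct.** Staff working from section 3.1 might give the WTP question at week 1, while staff working from section 3.6.2.3 would not. Someone reading the data later might then wonder whether an absent week 1 value was planned or missing.
- **Interpretation.** The purpose is a trajectory, and two points give one change. WTP data could not show whether movement between weeks 6 and 12 continued or reversed something earlier. The Background also names financial barriers as a reason for low hearing aid uptake, so WTP is not a trivial measure.

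**Working it through.** The protocol has no figure to reproduce here, so the check sets the schedules side by side.

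| Measure | Section | Week 1 | Week 6 | Week 12 |
|---|---|---|---|---|
| GHABP (primary) | 3.6.1.1 | yes | yes | yes |
| HHIE/HHIA | 3.6.2.1 | yes | yes | yes |
| HASS | 3.6.2.2 | yes | yes | yes |
| WTP | 3.6.2.3 | no | yes | yes |
| WHODAS 2.0 | 3.6.2.4 | yes | yes | yes |
| SADL | 3.6.2.5 | yes | yes | yes |
| CST | 3.6.2.6 | yes | yes | yes |

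**Extent.** There are 7 × 3 = 21 measure-by-week cells. Of these, 20 are scheduled and 1 is not. With the approximate 34 participants of section 3.3, and assuming full attendance, WTP gives 34 × 2 = 68 responses instead of 34 × 3 = 102. Both counts restate the same single absent time point and neither measures harm to a result. Nor does it help to say that 5 of the 11 weeks from week 1 to week 12 go unobserved for WTP, because no measure is taken between assessments, including those with three.

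**Is it a contradiction?** Section 3.1 does not say that all outcomes, or each outcome, are taken at every assessment. It can be read as the list of weeks at which assessments occur, and weeks 6 and 12 are both on that list. Where a general overview and a specific section differ in detail, the specific one is ordinarily followed. Section 3.6.2.3 names its two weeks plainly, so an absent week 1 WTP value is absent by schedule and is not missing data.

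**Does it spoil a result?** Write Y1, Y6 and Y12 for a participant's values at the three weeks. A three-point measure gives two successive changes, Y6 − Y1 and Y12 − Y6. WTP gives Y6, Y12 and Y12 − Y6. The summaries of those three quantities do not use Y1, so its absence leaves them unbiased and no less precise. Only Y1 itself and changes from week 1 are unavailable. Section 3.7 plans no statistical analysis, so no model or test depends on a week 1 WTP value, and the protocol states no WTP conclusion that would need it.

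**Is the purpose defeated?** The aim concerns longer-term outcomes over twelve weeks and does not promise three points for every measure. The primary outcome and five of the six secondary outcomes have all three. WTP keeps the two later ones.

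**The case for a change.** The strongest argument for acting is that the text cannot show whether the shorter schedule was chosen. The sentence in section 3.6.2.3 closely follows the one used for the other questionnaires, and its comma before the last week would fit a list that once began with week 1. The timing of an outcome belongs in the protocol, so this cannot be left to a statistical analysis plan. Repair would also be cheap: either one clause in section 3.1, or one short question at a week 1 assessment that takes place anyway.

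Part of this stands. A slip cannot be excluded, and a clause in section 3.1 noting the exception would make the document tidier. But a missing reason is not an error, since the protocol gives no reason for any of its assessment times. The comparison with HASS and SADL is suggestive only: those are rating scales, whereas WTP asks for a maximum dollar amount covering both devices and services. A price stated after one week rests on little use, which is a sensible ground for waiting even though the protocol does not offer it. Adding the question at week 1 would therefore be a preference about design and not a correction.

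**Conclusion.** The observation is accurate: WTP is the only measure without a week 1 assessment, section 3.1 does not mention this, and no reason appears. It does not call for a change. At most, section 3.1 is a loosely worded overview beside a specific section that can be followed as it stands.

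The cost is one time point on one of six secondary outcomes. WTP levels at weeks 6 and 12 and the change between them remain valid, early change in WTP cannot be described, and the primary outcome is untouched. If week 1 was dropped by accident, the loss is the same and still biases nothing.

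This rests on two assumptions: that staff follow the measure-specific schedule, and that reports of WTP make no claim about change before week 6. Any analyst would see the second from the two columns of data available.

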3.6.2.4 World Health Organization's Disability Assessment Schedule 2.0 (WHODAS 2.0)

The WHODAS is a questionnaire designed to measure quality of life. The summary score ranges from 0 (No disability) to 100 (Full disability). Participants will complete this questionnaire at 1-week, 6-week, and 12-week post-intervention based on their experience with the study device.

3.6.2.5 Satisfaction With Amplification in Daily Life (SADL)

The SADL is a questionnaire designed to measures subject's perceived hearing aid satisfaction. The score ranges from 1 (low satisfaction) to 7 (high satisfaction). Participants will complete this questionnaire at 1-week, 6-week, and 12-week post-intervention based on their experience with the study device.

3.6.2.6 Connected Speech Test (CST)

The CST is a speech recognition test designed to simulate daily speech communication. The score ranges from 0 (understand no speech) to 100 (understand all speech). Participants will complete this test in the laboratory at 1-week, 6-week, and 12-week post-intervention with the study device.

3.7 Statistical analysis

Because this is an exploratory study, no statistical analysis will be conducted.

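### The study sets out to explore how outcomes change over twelve weeks, but section 3.7 rules out any analysis of that change

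*Protocol*

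**What the plan says.** The Background (section 1) names the gap in evidence as the long-term outcomes of these devices and "whether these outcomes worsen, improve, or remain stable over time". Section 2 gives the purpose: "To explore the trajectory of long-term outcomes of OTC HAs over a period of twelve weeks".

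The design follows from that. Section 3.1 says "Outcomes will be measured at the first week, sixth week, and twelfth week post-HA use", and section 3.6.1.1 says of the Glasgow Hearing Aid Benefit Profile (GHABP): "The score at 1-week, 6-week and 12-week post intervention is the primary outcome". Five of the six secondary outcomes use the same three visits. The exception is willingness-to-pay (section 3.6.2.3): "Participants will complete this questionnaire at 6-week, and 12-week post-intervention". Section 3.3 does no power calculation, but states from experience that "approximately 34 participants are needed to see the trend of long-term HA outcomes".

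Section 3.7, in full, then says: "Because this is an exploratory study, no statistical analysis will be conducted". No other section provides for a summary, an estimate of change or an interval.

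**The concern.** The purpose, the visit schedule, the primary outcome and the reason for the sample size all concern change over time within the same people. Section 3.7 says that nothing will be done statistically with those measurements. The two cannot both be followed.

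The only reason given is that the study is exploratory. That is a sound reason for having no power calculation and no confirmatory test. It is not a reason for having no estimates, because estimation is how an exploratory study answers its question.

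At stake is whether the results can be interpreted. Outcomes may get better, get worse or hold steady. Without an estimate of change and an interval, a reader cannot separate steady outcomes from data too sparse to tell, or a real shift from sampling variation in about 34 people.

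**Working it through.** **The plan's own figure.** The sample size of about 34 can be neither reproduced nor refuted. Section 3.3 gives no significance level, power, effect size, standard deviation (SD) or dropout rate. There is no planned estimate or test to recompute.

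**The sections side by side.**

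| Section | What it commits to |
|---|---|
| 2 | Exploring the course of outcomes over twelve weeks |
| 3.1, 3.6.1.1 | Three repeated measurements per person, including the primary score |
| 3.3 | Enough participants for a trend to be visible |
| 3.7 | No statistical analysis |

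The first three rows need at least an estimate of change. The fourth excludes it.

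**How much uncertainty would go unreported.** Inputs from the protocol are n = 34 (section 3.3), the visits at weeks 1 and 12 (section 3.1) and the 0 to 5 GHABP range (section 3.6.1.1). The following are assumptions, because the protocol gives no values: all 34 people have both visits, the SD is the same at both visits, the between-visit correlation ρ is 0.3, 0.5 or 0.7, and the GHABP SD is 0.5 to 1.0 points.

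In units of the SD of the score:

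- Standard error (SE) of the mean change = √(2(1 − ρ)/34)
- 95% half-width = t(0.975, 33) × SE = 2.0345 × SE
- Chance that the observed mean change exceeds 0.2 SD in either direction when the true change is zero = 2(1 − Φ(0.2/SE)). The 0.2 SD threshold is chosen for illustration.

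| ρ | SE | 95% half-width | Chance of more than 0.2 SD with no true change |
|---|---|---|---|
| 0.3 | √(1.4/34) = 0.203 | 0.413 | 0.324 |
| 0.5 | √(1.0/34) = 0.171 | 0.349 | 0.243 |
| 0.7 | √(0.6/34) = 0.133 | 0.270 | 0.132 |

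A simulation of 40,000 studies of 34 participants gave 0.327, 0.245 and 0.132 for the last column.

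In GHABP points, the half-width runs from 0.270 × 0.5 = 0.135 to 0.413 × 1.0 = 0.413, so from about 0.14 to 0.41.

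**If some people drop out.** In units of the SD of the change itself, the half-width is t(0.975, n − 1)/√n. This is 0.349 with 34 completers, 0.373 with 30, 0.396 with 27 and 0.422 with 24. The completer numbers below 34 are illustrative.

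An estimate with an interval is therefore feasible at the planned size without any test or power calculation. The interval is also wide enough that an observed change should not be read without it.

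**The case against.** The strongest reply is that section 3.7 means only that no inferential testing is planned. Section 3.3 uses parallel wording to explain the missing power calculation, and it expects a trend to be seen, so some descriptive display is presumably intended. On that reading the fault is loose wording and a missing measure of precision. This does not remove the problem, because section 3.7 excludes statistical analysis as such and no other section supplies a summary or interval. It does limit the claim: the defect lies in what is planned, since the data will be collected and could still be summarised.

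A second reply is that an unseen statistical analysis plan may contain the analysis. The protocol is not silent, however. It states that there will be none, so a plan containing one would contradict section 3.7, which would still need correction.

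Other points stand as limits:

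- The question of whether outcomes change or hold steady comes from the Background, not from the Purpose. No stability margin is defined, so an interval shows which changes are compatible with the data but does not by itself establish stability.
- The numerical illustration rests largely on assumed values. It shows scale; the contradiction does not depend on it.
- A repeated-measures model is one choice among several. Visit means with paired changes and intervals would meet the same need. Using all available visits assumes that visits are missing at random, which is doubtful if people who stop using the device are also those who do not return, and a completer analysis does not cure that.
- Section 3.8 describes length of participation in the past tense, so data collection may already have been under way. This is an inference only.

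**Conclusion.** The concern holds. Section 3.7 affirmatively excludes the analysis that the purpose, the visit schedule and the sample-size rationale require, and exploratory status does not justify that. As written, the protocol plans no estimate of change and no statement of its precision.

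For scale, the unreported 95% interval for mean change from week 1 to week 12 would extend about 0.27 to 0.41 SD either side of the estimate. With no true change, the observed mean would still move by more than 0.2 SD in 13% to 32% of such studies. Both ranges assume 34 complete pairs, equal SDs and correlations from 0.7 down to 0.3.

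The section should be revised. The design and the three GHABP scores are usable as they are.

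**What to change.** Leave the choice of primary outcome in section 3.6.1.1 unchanged and replace section 3.7 with text such as:

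> The analysis is descriptive and no hypothesis test is planned. For GHABP, the mean within-participant change from week 1 to week 6 and from week 1 to week 12 will be estimated with 95% confidence intervals from a repeated-measures model with visit as a categorical factor, using all available visits. The paired change in participants with all three visits will be shown beside it, with the number measured at each visit. Secondary outcomes will be summarised in the same way, except willingness-to-pay, which is collected only at weeks 6 and 12, so its change is from week 6 to week 12.

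Three additions would make the text self-sufficient. It should identify the GHABP score analysed, given the four listening situations. It should state the missing-at-random assumption behind the model. If any outcome data have already been examined, it should say that the analysis was specified afterwards. Willingness-to-pay is a dollar amount and may be skewed, so its distribution should be shown alongside the mean.

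The cost is one reworded section and a small amount of analysis, with no new data, visits or participants. Including the secondary outcomes gives 6 × 2 + 1 = 13 intervals, unadjusted for multiplicity. They must be labelled descriptive and not read as tests.
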